9.7.4.2. Comparative analysis

Major congenital malformation outcomes

Major congenital malformations (any, each major malformation type, sample size permitting), among pregnancies ending in a live or a stillbirth pregnancy exposed to gabapentin during the first trimester will be compared against each of the comparators estimating crude and adjusted prevalence ratios in log-binomial regression.

In summary, the following comparative analyses will be performed:

- First-trimester gabapentin (monotherapy or polytherapy) vs. first-trimester unexposed to AEDs
- First-trimester gabapentin (monotherapy or polytherapy) vs. first-trimester pregabalin (monotherapy or polytherapy)
- First-trimester gabapentin (monotherapy or polytherapy) vs. first-trimester lamotrigine (monotherapy or polytherapy)
- First-trimester gabapentin (monotherapy or polytherapy) vs. first-trimester pregabalin or lamotrigine (monotherapy or polytherapy)

- First trimester gabapentin (monotherapy only) vs. first-trimester unexposed to AEDs
- First trimester gabapentin (monotherapy only) vs. first-trimester pregabalin (monotherapy only)
- First trimester gabapentin (monotherapy only) vs. first-trimester lamotrigine (monotherapy only)
- First-trimester gabapentin (monotherapy only) vs. first-trimester pregabalin or lamotrigine (monotherapy only)

Prevalence ratios comparing the frequency of major congenital malformations in patients with first-trimester gabapentin exposure (monotherapy or polytherapy) and patients with no first-trimester exposure to AEDs will be estimated within the <1.0, 1.0-2.0, and >2.0 DDD categories; however these estimates are likely to be unstable due to small counts.

Birth outcomes other than major congenital malformations

For birth outcomes other than major congenital malformations, any-trimester gabapentin exposed births will be compared against each of the comparators estimating crude and adjusted prevalence ratios in log-binomial regression.

To summarise, the following comparative analyses will be performed for all outcomes:

- Any-trimester gabapentin (monotherapy or polytherapy) vs. any-trimester unexposed to AEDs
- Any-trimester gabapentin (monotherapy or polytherapy) vs. any-trimester pregabalin (monotherapy or polytherapy)
- Any-trimester gabapentin (monotherapy or polytherapy) vs. any-trimester lamotrigine (monotherapy or polytherapy)
- Any-trimester gabapentin (monotherapy or polytherapy) vs. any-trimester pregabalin or lamotrigine (monotherapy or polytherapy)

- Any-trimester gabapentin (monotherapy only) vs. unexposed to AEDs
- Any-trimester gabapentin (monotherapy only) vs. any-trimester pregabalin (monotherapy only)
- Any-trimester gabapentin (monotherapy only) vs. any-trimester lamotrigine (monotherapy only)

- Any-trimester gabapentin (monotherapy only) vs. any-trimester pregabalin or lamotrigine (monotherapy only)

9.7.5. Secondary analyses

The secondary analyses will be conducted among live-born children. In these analyses any trimester gabapentin exposure will be considered versus each of the comparators as above. The monotherapy subset will be examined, sample size permitting.

Incidence rates (number of events/person-time contributed by live-births) of the postnatal neurodevelopmental outcomes will be reported according to any prenatal exposure to gabapentin and the predefined comparators. All incidence rates will be reported for any gabapentin therapy and the subset with gabapentin monotherapy.

For the postnatal neurodevelopmental outcomes, exposure will be defined at any time during pregnancy. Crude and PS-adjusted hazard ratios will be estimated using Cox's proportional-hazards regression. In the event that too few postnatal outcomes are observed to estimate association, the number of cases and crude rates will be reported to the extent allowed by the data protection regulation.

To summarise, the following comparative analyses will be performed for all outcomes:

- Any-trimester gabapentin (monotherapy or polytherapy) vs. any-trimester unexposed to AEDs
- Any-trimester gabapentin (monotherapy or polytherapy) vs. any-trimester pregabalin (monotherapy or polytherapy)
- Any-trimester gabapentin (monotherapy or polytherapy) vs. any-trimester lamotrigine (monotherapy or polytherapy)
- Any-trimester gabapentin (monotherapy or polytherapy) vs. any-trimester pregabalin or lamotrigine (monotherapy or polytherapy)

Sample size permitting:

- Any-trimester gabapentin (monotherapy only) vs. unexposed to AEDs
- Any-trimester gabapentin (monotherapy only) vs. any-trimester pregabalin (monotherapy only)
- Any-trimester gabapentin (monotherapy only) vs. any-trimester lamotrigine (monotherapy only)
- Any-trimester gabapentin (monotherapy only) vs. any-trimester pregabalin or lamotrigine (monotherapy only)

9.7.6. Sensitivity analyses

To evaluate the potential bias in the analysis of major congenital malformations from excluding pregnancies terminated due to known malformations, a sensitivity analysis including these terminated pregnancies will be conducted in the countries where this information is available (Denmark, Norway and Finland). The sensitivity analyses will be conducted in the following study population/analysis set: singleton/multiple live births, stillbirths, or pregnancies ending in therapeutic 2nd trimester induced abortion (these will be considered singleton pregnancies). The analyses in this population will assess the association of the first-trimester exposure to gabapentin and major congenital malformations (overall, not for specific malformations due to expected low counts), including all the comparators above. Separate descriptive tables will be produced, and separate sets of PS will be estimated as appropriate for each contrast in the sensitivity analyses.

All estimates of association will be reported with appropriate 95% confidence intervals (CIs).

In the primary analyses, patients with at least one dispensing within the relevant timeframe will be classified as exposed. However, some patients may have obtained a single dispensing (prescription) of an antiepileptic drug. Possible reasons for this may be that the drug was

prescribed for an indication other than epilepsy, treatment was stopped due to an adverse reaction, etc. Two (2) gabapentin dispensing categories of '1 dispensing', and '>1 dispensing', will be used to stratify select descriptive analyses of major congenital malformations (it is anticipated that patient counts will not be high enough to support stratified comparative analyses). The number of major congenital malformation events, the total number of newborns at risk and the prevalence of major congenital malformation events for each of the 2 gabapentin dispensing categories will be provided. As noted above, given the very small sample size of gabapentin first trimester-exposed pregnancies ending in a live or still birth, and the low prevalence of major congenital malformations, it will not be feasible to conduct any further stratified analyses (i.e., analyses simultaneously stratified by dispensing and other variables).

9.7.7. Combining results

Crude and adjusted estimates of association from Sweden, Norway, and Finland will be transferred to Aarhus University, Aarhus, Denmark for meta-analyses or other combined analyses. Because of the similarities between the healthcare systems in the Nordic countries and the use of a common study protocol with well-defined selection of exposures, outcomes and covariates, a fixed-effects meta-analysis is justifiable applied.⁵⁵ Country-specific crude and adjusted estimates of association for each prespecified comparison will first be calculated and presented. These results will then be combined in a meta-analysis, or, if deemed more suitable, another method that allows incorporation into combined estimates of associations with no exposed events, such as Mantel-Haenszel pooling methods.⁵⁶ For each outcome the coordinating centre will use the inverse variance method in the fixed effects meta-analyses, which is weighting the country-specific estimates of association by the inverse of the within-country variances. Homogeneity of the estimates will be verified, and a random-effects meta-analysis will be considered as an alternative should the estimates be found to be heterogeneous. The rejected model, i.e. the model not used as the primary model, will be checked in a sensitivity analysis. For example, if the fixed-effect model is used as the primary meta-analytical approach, the random-effects model will be checked in a sensitivity analysis, and vice versa. Results of combined analyses will be presented using a standard forest plot, reporting the country-specific overall crude and adjusted point estimates, and the pooled overall crude and adjusted point estimates, all with 95% CIs.

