9.5. Study size

Table 3 shows estimated number of total pregnancies ending in live or stillbirth and pregnancies with AED exposure (any use, i.e., pregnancies exposed to monotherapy and pregnancies exposed to polytherapy).

Table 3. Estimated numbers of pregnancies ending in live or still birth (any use, i.e., pregnancies exposed to monotherapy and pregnancies exposed to polytherapy)*

	Denmark (2005-2016)	Finland (2005-2016)	Norway (2005-2016)	Sweden (2006-2016)	TOTAL
Live/still births	728,052	701,550	717,219 (657,451)	1,152,002	3,298,823

Table 3. Estimated numbers of pregnancies ending in live or still birth (any use, i.e., pregnancies exposed to monotherapy and pregnancies exposed to polytherapy)*

	Denmark (2005-2016)	Finland (2005-2016)	Norway (2005-2016)	Sweden (2006-2016)	TOTAL
Pregnancies with dispensation of Gabapentin, first trimester	374	374	344	500	1,592
Gabapentin, any time during pregnancy	388	388	467	500	1,743
Pregabalin, first trimester	372	1,020 (935)	248 (227)	1,230	2,870
Pregabalin, any time during pregnancy	377	1,053 (965)	225 (307)	1,275	2,930
Lamotrigine, first trimester	2,266	1,048 (961)	1,841 (1,688)	2,838	7,993
Lamotrigine, any time during pregnancy	2,379	1,104 (1,012)	2,110 (1,934)	2,991	8,584

*Number of exposed in Denmark and Sweden are the actual numbers for 2005-2016; estimated for Finland and Norway based on 2005-2015 data in parenthesis. No exclusion criteria are applied in this table.

The 2005-2016 estimated numbers of pregnancies ending in live or still birth for potentially analysis-relevant categories for Norway and Finland were unavailable at the time of writing the protocol but are estimated using data from 2005-2015 to provide the most conservative estimate.^{14,45,46,47}

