9.7. Data analysis

For all data analyses, the birth (not the patient/mother) will be the unit of analysis. Given that a woman could have more than one birth during the study period, data analyses will account for correlated observations using GEE (generalized estimating equation) or robust variance estimates. All steps of the country-specific data analyses will be conducted separately in each participating country according to the description below. Each country will generate a set of identical analytic tables. Registry data will not be provided for very low numbers (less than 5 events) due to data security and data confidentiality rules.

After conducting the country-specific data analyses, country-specific datasets containing crude and adjusted estimates of association will be transferred to Aarhus University Hospital, Denmark, for meta-analyses.

Given that gabapentin has several indications and that administrative data available for this study have low sensitivity in identifying relevant indications for all pregnancies, in this study pregnancies exposed to gabapentin will be compared with pregnancies exposed to medications with similar sets of indications. Because confounding by indication or severity

of indication may persist even against an active comparator,⁷ the amount of confounding may be inferred indirectly by examining whether estimates of association differ depending on the comparator. Here, pregabalin and lamotrigine, which are both indicated for epilepsy, have been identified as suitable active comparators.

In a 2019 publication from Sweden, all individuals aged 15 years or older and being dispensed at least 2 prescriptions of gabapentin in the period 2006-2013 were identified (N=85,360).⁴⁹ The indication of use (i.e. health status before start of treatment) was 6.4% epilepsy, 20% psychiatric disorders, and 52.1% musculoskeletal disorders. In the same publication, the indication of use for pregabalin (n=120,664) was 5.4% epilepsy, 40.9% psychiatric disorders, and 46.2% musculoskeletal disorders. Published data on the most common gabapentin indication in pregnant women are unavailable at this time.

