The defined daily dose (DDD) of gabapentin is 1800 mg.⁵³ In the EU, the recommended/approved daily dose of gabapentin is 900-3600 mg⁵⁴ (equivalent of 0.5-2.0 times the DDD). Three (3) gabapentin cumulative dose (DDD) categories of < 1.0, 1.0-2.0, and > 2.0 times the DDD, will be used to stratify select descriptive analyses of major congenital malformations. The number of major congenital malformation events, the total number of newborns at risk and the prevalence of major congenital malformation events for each of the 3 gabapentin dose categories will be provided. In the study feasibility assessment, even after combining available data from the 4 Nordic countries to obtain a total of 3,298,823 first trimester exposed pregnancies ending in live or still birth, a conservative estimate of 1,592 gabapentin first trimester-exposed pregnancies ending in live or still birth were determined to be available (see Table 3). Given this very small sample size, and the low prevalence of major congenital malformations, it will not be feasible to conduct any extensive stratified analyses (i.e., analyses simultaneously stratified by dose and other variables) or dose dependency analyses. In addition, dose-stratified analyses on the combined dataset will not be possible since data will not be combined at the individual level.

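### Default inverse-variance pooling biases rare-outcome ratios upward against the AED-unexposed and lamotrigine groups, and the Mantel-Haenszel alternative has neither a trigger nor a secured supply of counts

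*Protocol*

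**What the plan says.** Protocol section 9.7.7 justifies a fixed-effect meta-analysis of country results and then fixes the weights: "For each outcome the coordinating centre will use the inverse variance method in the fixed effects meta-analyses". If judged preferable, the results may be combined instead by "another method that allows incorporation into combined estimates of associations with no exposed events, such as Mantel-Haenszel pooling methods". No rule says when that judgement is made or on what count. Random effects is the alternative if the estimates look heterogeneous, and the model not chosen is run as a sensitivity analysis.

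On what reaches the coordinating centre, section 9.7 says "country-specific datasets containing crude and adjusted estimates of association will be transferred to Aarhus University Hospital, Denmark, for meta-analyses", and section 9.7.7 says "Crude and adjusted estimates of association from Sweden, Norway, and Finland will be transferred to Aarhus University, Aarhus, Denmark". Section 9.7 adds: "Registry data will not be provided for very low numbers (less than 5 events) due to data security and data confidentiality rules". Section 9.7.4.1 states that "data will not be combined at the individual level". Each country ratio comes from log-binomial regression with a Wald interval (section 9.7.3).

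**The concern.** The variance of a log ratio is driven by the smaller event count, here the exposed one. When each country has only a handful of exposed events, inverse-variance weights are nearly the observed counts themselves. A country with a chance excess gains weight, one with a chance deficit loses it, and one with no exposed event has no finite ratio and drops out. All three push the pooled ratio the same way. The random-effects alternative works on the same country estimates, so it does not bring a zero-event country back.

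This is a post-authorisation safety study committed to the EMA. Stillbirth is a primary outcome, and specific malformations are in the primary comparative analysis where numbers allow. A default that leans upward under no effect produces extra apparent harm signals. An untriggered alternative would be chosen after the estimates are known.

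**Working it through.** **Inputs.** Exposed births for Denmark, Finland, Norway and Sweden, from Table 3: 374, 374, 344, 500 in the first trimester (total 1,592) and 388, 388, 467, 500 at any time (total 1,743). Births: 728,052; 701,550; 717,219; 1,152,002 (total 3,298,823). Prevalences are those of Table 4. The true ratio is 1.0, as section 9.5 assumes.

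**The plan's own figure.** Table 4 follows from exp[(1.960 + 0.842) × √((1−p)/(n₁p) + (1−p)/(n₀p))]. For 0.6% against unexposed, n₁p = 1,743 × 0.006 = 10.458 and n₀p ≈ 19,782. The root is √(0.994/10.458 + 0.994/19,782) = 0.308, and exp(2.802 × 0.308) = 2.37; unrounded, 2.373 as printed. The 0.2%, 1%, 3% and 10% rows reproduce too (4.801, 1.950, 1.465, 1.223). This formula treats the four countries as one table using every event, so it cannot reveal a pooling problem.

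**Why the bias has one direction against a very large comparator.** Let country i have aᵢ exposed events and eᵢ expected. The variance of log(aᵢ/eᵢ) is about 1/aᵢ, so the weight is about aᵢ and the pooled log ratio is Σaᵢ log(aᵢ/eᵢ) / Σaᵢ. By the log-sum inequality this is never below log(Σaᵢ/Σeᵢ).

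**Illustration, 0.6%, any-time counts.** Expected events are 2.33, 2.33, 2.80 and 3.00 (total 10.46).
- Observed 1, 2, 3, 5: total observed/expected is 11/10.46 = 1.05. The country ratios 0.43, 0.86, 1.07, 1.67 get weights 1.00, 2.01, 3.02, 5.05, and the pooled ratio is 1.16.
- Observed 0, 2, 3, 6: same total, 1.05. Denmark drops out and the pooled ratio is 1.45.
- Mantel-Haenszel gives 1.05 in both cases.

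**Simulation.** 400,000 data sets per scenario, binomial counts per country, true ratio 1. Inverse variance on Wald log ratios, with zero-event countries dropped, is compared with Mantel-Haenszel with Wald limits. Ranges show variation between runs. Against AED-unexposed:

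| Prevalence (window) | Expected exposed events per country | At least one country with zero | Inverse-variance median | Lower limit above 1 | Mantel-Haenszel median | Lower limit above 1 |
|---|---|---|---|---|---|---|
| 0.2% (first trimester) | 0.7–1.0 | 91% | 1.76–1.77 | 17% | 0.94 | 4.5–4.6% |
| 0.6% (any time) | 2.3–3.0 | 27% | 1.17 | 8.5% | 0.96 | 3.8% |
| 1% (first trimester) | 3.4–5.0 | 8% | 1.10 | 6.8% | 1.00 | 3.5% |
| 3% (first trimester) | 10–15 | about 0% | 1.03 | 4.7% | 1.00 | 2.8% |

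The nominal value for a lower limit above 1 is 2.5%.

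Inverse variance against the active comparators, same prevalences and windows:

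| Comparator | Medians | Lower limit above 1 |
|---|---|---|
| Lamotrigine | 1.78 / 1.16 / 1.09 / 1.02 | 8.0 / 5.2 / 4.6 / 3.7% |
| Pregabalin or lamotrigine | 1.83 / 1.16 / 1.09 / 1.03 | 11.1 / 6.1 / 5.2 / 4.0% |
| Pregabalin | 1.33 / 1.04 / 1.03 / 1.01 | 0.8 / 1.6 / 2.0 / 2.5% |

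**Counts for the alternative.** The chance that a given country's exposed count is below 5 is at least 99.6% at 0.2%, 82–91% at 0.6% and 44–74% at 1% (first trimester). All four are below 5 in 99% of data sets at 0.2% and 58% at 0.6%.

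**The case against.** The protocol foresees countries with no exposed events and names Mantel-Haenszel for them, so the authors were aware of part of the problem. A trigger could be left to an analysis plan. That has weight, but the default is stated here for each outcome, and the bias does not need a zero: in the illustration 1, 2, 3, 5 already gives 1.16 instead of 1.05.

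A reader might infer that Mantel-Haenszel cannot run at all on what the countries send. The documents do not go that far. Neither section says that nothing but estimates is transferred. Countries produce identical analytic tables, section 9.7.7 also allows for other combined analyses, and the under-5 rule does not say whether it binds transfers between investigators or only released results. What stands is that the needed counts are not secured.

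A reader might also infer a general upward bias for every comparator and outcome. That fails too. Against pregabalin at 0.6% and above the median is 1.04 or less and exceedance is at or below nominal. At a true ratio of 2 the bias there is slightly downward (median 1.89 at 0.6%). Preterm birth/SGA and any major malformation are barely affected.

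Two further points hold. Comparisons by malformation type depend on adequate numbers (section 9.7.4.2), and postnatal outcomes fall back to counts and crude rates when events are too few (section 9.7.5), so the 0.2% row may never be reported. And Mantel-Haenszel with Wald limits also exceeds 2.5%, so part of the inverse-variance excess is ordinary small-count behaviour that changing the pooling method would not remove.

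**Conclusion.** The point holds for rare outcomes against AED-unexposed, lamotrigine, and the combined comparator. The case that matters most is stillbirth: it is an unconditional primary outcome, with a median pooled ratio of 1.17 against unexposed under no effect and a lower limit above 1 about 8.5% of the time, against 3.8% with Mantel-Haenszel. At 0.2% the distortion is large (about 1.77) but conditional on those comparisons being made. At 1% it is modest (1.10), and at 3% negligible (1.03).

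The sizes rest on crude binomial counts without propensity weighting or clustering of repeat births, on Table 3 counts before exclusions, and on Table 4 prevalences common to all countries. Postnatal outcomes are analysed by Cox regression, which was not simulated; only the weighting mechanism carries over. The plan should be changed, but the main any-malformation result is not threatened.

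**What to change.** In section 9.7.7, name a count-based pooled method as primary for stillbirth, specific malformations and any other outcome with low expected exposed events per country: Mantel-Haenszel on crude and propensity-weighted counts, with a variance that allows for the weights and for repeat births. State the threshold in expected events and fix it before the data are seen. Keep inverse variance for the commoner outcomes.

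In sections 9.7 and 9.7.7, state that each country also transfers the Mantel-Haenszel numerator, denominator and variance terms under an agreed small-cell arrangement. If a custodian refuses, the country sends a penalised log ratio with its standard error, which stays finite at zero events; this fallback was not simulated here and should be checked before adoption.

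The cost is a few extra aggregate columns per country, a wording change and custodian clearance, best sought before extraction. No new data are needed.

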9.8. Quality control

Data storage, management and analyses will be conducted according to each institution's standard procedures. At a minimum, all study documents (protocol, report, publications) will be reviewed by the entire research team. A senior epidemiologist in each institution will review the report before submission to the sponsor. Clinical expertise is available for appropriate interpretation of results. At the start of the project, a kick-off meeting will establish a regular communication plan (via e-mail and regular teleconferences); and internal timelines will be established to allow review and quality control before submitting each deliverable. Each institution will also follow its internal quality control procedures and will ensure the necessary compliance with local data protection, storage and archiving, and

patient privacy laws and regulations and will obtain all permission necessary to conduct this study.

